Fifty-nine subjects (26.0%) prematurely discontinued study drug; 57 subjects (25.1%) discontinued study drug before 48 weeks of dosing. The most common reasons for discontinuation of study drug were perceived lack of efficacy (12.3%) and laboratory abnormalities or TEAEs (8.4%). Overall, more subjects treated with BCX7353 110 mg compared to BCX7353 150 mg discontinued study drug due to perceived lack of efficacy; 17 of 100 subjects (17.0%) vs. 11 of 127 subjects (8.7%). Overall, 19 subjects (8.4%) discontinued study drug due to TEAEs; 6 (6.0%) and 13 subjects (10.2%) in the BCX7353 110 and 150 mg

dose groups, respectively. TEAEs leading to discontinuation in > 1 subject were ALT increased (4 subjects [1.8%]), upper abdominal pain (3 subjects [1.3%]), vomiting (2 subjects [0.9%]), AST increased (2 subjects [0.9%]), hepatic enzyme increased (2 subjects [0.9%]), and liver function test (LFT) abnormal (2 subjects [0.9%]).

The majority of subjects (91.0% and 90.6% of subjects in the BCX7353 110 and 150 mg dose groups, respectively) had at least 1 TEAE during the study. There was no effect of dose on the incidence of AEs. Overall, the most frequently reported TEAEs were nasopharyngitis (30.8%), headache (17.6%), abdominal pain (13.2%), and diarrhea (13.2%).

Long term prior androgen use of ≥ 5 years and discontinuation of androgens within 2 weeks of BCX7353 initiation were correlated with a higher subject incidence of liver-related TEAEs, but not other types of TEAEs. Subjects who discontinued androgens in the 2 weeks prior to initiating BCX7353 (n = 40) experienced liver-related TEAEs in the investigations SOC more frequently than subjects who discontinued androgens ≥ 2 weeks before initiating BCX7353 (n = 113) or those subjects who had never used androgens (n = 74). In these groups, ALT increased, 25.0% vs. 2.7% and 1.4%, respectively; AST increased 17.5% vs. 2.7% and 1.4%, respectively; hepatic enzyme increased, 2.5% vs. 0.9% and 0, respectively; LFT abnormal, 5.0% vs. 0 and 0; and transaminase increased, 2.5% vs. 0 and 0.

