5.7. Overall Benefit-Risk Assessment

The risks from daily oral administration of BCX7353 seen to date in both preclinical and clinical studies were primarily mild, monitorable, and reversible. Overall, the clinical efficacy and safety data support a favorable benefit risk profile for BCX7353. In the 24-week, adequate, well-controlled pivotal efficacy and safety trial in adolescents and adults with Type I or II HAE, BCX7353 150 mg QD treatment for 24 weeks versus placebo resulted in statistically significant and clinically meaningful reductions in monthly HAE attack rate, monthly rate of HAE attacks requiring acute rescue therapy, the monthly rate of moderate or severe HAE attacks, and the monthly rate of laryngeal HAE attacks. Results of sensitivity and subgroup analyses of the HAE attack rate were consistent with those of the primary efficacy analysis. The safety data from controlled trials and long-term open-label studies is sufficient to assess the safety of BCX7353 in the proposed rare disease HAE population. Important potential risks are delayed-type hypersensitivity reactions (rash) and transaminase elevations. Hypersensitivity rash was identified as a signal early in development; few events were reported, and these were mild to moderate, self-limited, not dose dependent, and resolved with continued dosing without recurrence. Increases in ALT/AST were generally transient, asymptomatic, not dose dependent, and heavily confounded by prior administration of androgens. The overall benefit-risk balance is therefore considered to be acceptable.

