#### **9.3.1. Summaries of Adverse Event Incidence Rates for All Subjects and Adverse Incidence Rates for Serious Adverse Events, Adverse Event Dropouts, and Death**

A brief summary of AEs will show, by treatment group, the number and percentage of subjects who 1) had any AE, 2) had any drug-related event, 3) permanently discontinued from study drug due to an AE, 4) had any serious adverse event (SAE), 5) had any Grade 3 or higher AE, 6) had any Grade 3 or higher drug-related AE, 7) had any AE leading to interruption of study drug, 8) had a drug-related SAE, or 9) had a fatal SAE.

AEs will be summarized by treatment group. For each SOC and PT, the number and percentage of subjects reporting an event will be calculated. In summary tables, SOC and events within a SOC will be presented by decreasing frequency count based on the total number of events. Multiple events (by subject or SOC as appropriate) will be counted only once per subject per dose in each summary. For summaries that use severity grade, the most severe event will be selected.

The following summary tables (number and percentage of subjects) of TEAEs (by SOC and PT) will be provided by treatment group:

- Overall summary of TEAEs
- Summary of TEAEs
- Summary of drug-related TEAEs
- Summary of treatment-emergent adverse events by severity
- Summary of Grade 3 or Grade 4 TEAEs
- Summary of drug-related, Grade 3 or Grade 4 TEAEs
- Summary of TESAEs
- Summary of TEAEs leading to permanent discontinuation of study treatment
- Summary of TEAEs leading to interruption of study treatment
- Summary of drug-related, TESAEs

In addition, summaries of frequent TEAEs and drug-related TEAEs will be provided by preferred term (not by SOC and PT), in decreasing order of frequency. Frequent TEAEs will be defined as TEAEs that occur in at least 5% of the total number of subjects in the clinical trial. The number of events will be displayed on all summary tables except the overall summary of TEAEs. All TEAE analyses will be repeated using subgroups.

A single presentation of the summary of TEAEs for subjects entering on prophylactic medications will be presented. For this presentation, only TEAEs occurring while the subject was simultaneously taking BCX7353 and prophylactic medication will be summarized.

Data listings will be provided for all AE data. In addition to listing all AEs, distinct data listings will also be provided for the following:

- Grade 3 or Grade 4 AEs

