### **9.3.3. Gastrointestinal Abdominal-Related AEs**

Gastrointestinal (GI) abdominal-related AEs are also of interest, although these are not AEs of special interest for investigator reporting purposes. There are no appropriate standard MedDRA queries (SMQs) to evaluate abdominal-related AEs that are appropriate to assess potential adverse events associated with BCX7353 use. In order to create a list of PTs that are pertinent, the events to be analyzed have been prospectively defined as all PTs within the MedDRA 19.1 hierarchy under the High Level Group Terms (HLGTs) of 1) gastrointestinal signs and symptoms and 2) gastrointestinal motility and defaecation conditions (See Section 13.3 for a detailed list of PTs High Level Terms, and HLGTs). This selection is broad enough so that GI events are appropriately identified and analyzed but excludes terms that, although in the GI SOC, are not representative of the events of concern such as oral or esophageal events.

For the GI abdominal-related events, separate listings will be provided. In addition, for GI abdominal-related events there will be a summary that shows, by treatment group, the number and percentage of subjects with:

- A TEAE
- A drug-related TEAE
- Permanent discontinuation from study drug due to the TEAE
- An AE that was considered an TESAE
- Any Grade 3 or higher TEAE
- Any Grade 3 or higher drug-related TEAE

- Any TEAE leading to interruption of study drug
- An TEAE that was considered a drug-related TESAE
- A TEAE that required use of concomitant medication

For treatment-emergent GI abdominal-related AEs, time to development of the AE will be estimated using the Kaplan-Meier method. The results will be displayed in summary tables as well as in a Kaplan-Meier plot. Subjects who do not experience the event of interest will be censored at the date of the last dose. Summary displays for the GI abdominal-related TEAEs will include a count of the number of AEs as well as the number of subjects who experience each AE.

A Kaplan-Meier plot and summary of duration of event will be provided for GI abdominal-related TEAEs. The summary display will provide the median duration of event by treatment group, with the event as the unit of interest rather than the subject.

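### SAP 9.3 plans no grouped summary of liver adverse events, although transaminase elevation is one of two named important potential risks

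*SAP*

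**What the plan says.** - **The risk.** Protocol 5.7: "Important potential risks are delayed-type hypersensitivity reactions (rash) and transaminase elevations".
- **Adverse event tables.** SAP 9.3.1: "For each SOC and PT, the number and percentage of subjects reporting an event will be calculated". This layout serves the tables of all, drug-related, Grade 3 or 4, serious, interrupting and discontinuing TEAEs, and they are repeated by the androgen subgroups of SAP 9.2. A subject counts once per row. A further table shows only terms reaching 5% of subjects.
- **GI abdominal events.** SAP 9.3.3 defines a group of PTs in advance (listed in 13.3) and adds a subject-level table: "In addition, for GI abdominal-related events there will be a summary that shows, by treatment group, the number and percentage of subjects with". The rows cover any event, a related one, a serious one, one of Grade 3 or higher, and one leading to interruption or discontinuation.
- **Rash.** SAP 9.3.2 uses the same layout, but rash is identified by an investigator flag on the adverse event form, not by a term list.
- **Liver laboratory values.** SAP 9.6 plans multiples of the upper limit of normal (ULN) for ALT, AST, bilirubin and ALP, transaminase criteria combined with bilirubin, Kaplan-Meier times to Grade 3 or higher values and a Hy's law plot, with the table of hepatic abnormalities repeated by androgen subgroup.
- **Planned displays.** The list in SAP 13.1 has no table of grouped liver TEAEs.
- **Interim results.** Protocol 5.2.2 discusses liver-related TEAEs as a class but gives figures only by term, for subjects who stopped androgens within 2 weeks of starting BCX7353, those who stopped earlier, and never-users: "In these groups, ALT increased, 25.0% vs. 2.7% and 1.4%, respectively". The matching figures, in the same order of groups, are 17.5%, 2.7% and 1.4% for AST increased; 2.5%, 0.9% and 0 for hepatic enzyme increased; 5.0%, 0 and 0 for LFT abnormal; and 2.5%, 0 and 0 for transaminase increased.

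**The concern.** When one harm is coded under several PTs, each row is smaller than the whole, and the rows cannot be added because one subject may appear in several. The number of subjects affected is then lost unless the terms are grouped.

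Two of the study's safety endpoints are Grade 3 or 4 TEAEs and discontinuation for a TEAE. For one of the two named risks, the planned tables would show how often these occurred only in pieces, while GI abdominal events would have a single figure. A reader setting the two side by side would be comparing a group with fragments.

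The class is also already in use without a definition. Protocol 5.2.2 concludes that long androgen use and recent androgen withdrawal go with a higher subject incidence of liver-related TEAEs, and of Grade 3 or 4 ones. Protocol 5.4.3 expects the study to inform guidance on switching from androgens. The SAP contains neither the term list nor the table behind such a statement.

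**Working it through.** **Inputs.** All from Protocol 5.2.2: group sizes 40, 113 and 74 (40 + 113 + 74 = 227), the percentages quoted above, the liver terms among TEAE discontinuations (ALT increased 4, AST increased 2, hepatic enzyme increased 2, LFT abnormal 2), all TEAE discontinuations (19), and GI abdominal discontinuations (6).

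**Step 1: reproduce the stated figures.** 4/227 = 1.8%, 2/227 = 0.9%, 19/227 = 8.4% and 6/227 = 2.6%, as printed. Each PT percentage converts to a whole count:

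| Term | < 2 weeks (n = 40) | ≥ 2 weeks (n = 113) | Never (n = 74) | Total of 227 |
|---|---|---|---|---|
| ALT increased | 10 | 3 | 1 | 14 (6.2%) |
| AST increased | 7 | 3 | 1 | 11 (4.8%) |
| Hepatic enzyme increased | 1 | 1 | 0 | 2 (0.9%) |
| LFT abnormal | 2 | 0 | 0 | 2 (0.9%) |
| Transaminase increased | 1 | 0 | 0 | 1 (0.4%) |

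Only ALT increased passes the 5% threshold of the frequent-TEAE table.

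**Step 2: bound the number of subjects with any of the five terms.** The lower limit is the largest single row (full overlap). The upper limit is the sum of the rows (no overlap).

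- < 2 weeks: 10 to 10 + 7 + 1 + 2 + 1 = 21 of 40, or 25.0% to 52.5%.
- ≥ 2 weeks: 3 to 3 + 3 + 1 = 7 of 113, or 2.7% to 6.2%.
- Never used: 1 to 1 + 1 = 2 of 74, or 1.4% to 2.7%.
- Overall: 10 + 3 + 1 = 14 to 21 + 7 + 2 = 30 of 227, or 6.2% to 13.2%.

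**Step 3: the same for discontinuation.** Lower limit 4; upper limit 4 + 2 + 2 + 2 = 10. That is 1.8% to 4.4% of 227, or 4/19 = 21% to 10/19 = 53% of the TEAE discontinuations. The protocol lists only terms that led more than one subject to stop, so single-subject liver terms could raise the upper limit.

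**Step 4: the same for Grade 3 or 4.** ALT increased 2.6%, hepatic enzyme increased 0.9% and LFT abnormal 0.9% correspond to 6, 2 and 2 subjects. The range is 6 to 10 of 227, or 2.6% to 4.4%. Other terms at this grade occurred in one subject each, so the top could again be slightly higher.

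**Step 5: can the laboratory tables stand in?** In the < 2-week group, ALT above 3 × ULN was seen in 32.5% (13 of 40), against 10 of 40 with the term ALT increased. The two sources count different things, and the laboratory tables do not record why drug was interrupted or stopped.

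**The case against.** The strongest reply is that the named risk is a laboratory one and that SAP 9.6 measures it better than adverse event terms can: values are scheduled and centrally analysed, whereas a result becomes an adverse event only if the investigator judges it clinically significant (Protocol 11.1.6). This stands. A reader might infer from the adverse event tables that the plan has no proper liver analysis, and SAP 9.6 shows that this is not so. It does not supply relatedness, seriousness, interruption or discontinuation. Outside the criteria combined with bilirubin, it also lists ALT and AST separately.

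Second, the Investigations SOC row counts each subject once, and Protocol 5.2.2 places the five terms there. For discontinuation it may come close, because every investigations-type term shown for more than one subject is a liver term. It still mixes in non-liver tests and misses hepatic terms coded to another SOC. Listings 16.2.7.4 and 16.2.7.9 would allow a hand count of discontinuations, but against no predefined list.

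Third, SAP 9.3.3 gives a reason for grouping GI terms, namely that no suitable standard query exists, and symptoms have no laboratory marker. That explains the GI list; it does not argue against one for the liver. The rash summary is not a second example of term grouping, since it rests on a flag.

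Fourth, the group with the largest figures, androgens stopped less than 2 weeks before, should not grow under the current 28-day washout. Those subjects do remain in the final data.

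**Conclusion.** The point holds as a gap in the adverse event summaries, not in liver monitoring or the laboratory analysis. From the figures reported by term, the proportion with any of the five liver terms can be placed only between 6.2% and 13.2%, about a twofold range that comes purely from tabulation. Discontinuation for a liver term lies between 4 and 10 subjects, a range that includes the 6 for GI abdominal events.

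Two stronger readings are not supported. A reader might take the upper limits as likely values; they require that no subject had two of the terms, for example both ALT increased and AST increased. A reader might also infer that liver events were the leading reason for stopping. The documents do not settle this: at the lower limit liver falls below GI. Of the 13 subjects with Grade 3 or 4 ALT, 5 improved or recovered while continuing drug, but the text does not say whether the other 8 stopped or only interrupted.

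The result assumes that the rounded percentages convert to whole counts, which they do, and that the five reported terms are the relevant ones. Hepatic terms outside the Investigations SOC are not shown and could add subjects. This is a cheap improvement worth making; it does not undermine the study's safety conclusions.

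**What to change.** Add a subsection to SAP 9.3 that defines a liver-related TEAE by a fixed MedDRA 19.1 term list, set out in an appendix as 13.3 does for GI events. The list should hold at least ALT increased, AST increased, hepatic enzyme increased, LFT abnormal and transaminase increased, plus hepatic disorder terms coded outside Investigations.

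Report the group with the 9.3.3 per-subject summary (any, drug-related, Grade 3 or higher, serious, leading to interruption, leading to discontinuation), overall and by the androgen latency and duration subgroups of 9.2. Add the tables to 13.1.

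The cost is one term list and one extra table set on an existing layout, with no new data. The drawback for the sponsor is that the headline liver rate can be no more favourable than any single-term row. The change affects analysis only and sets no clinical rule.

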9.7. Concomitant Medications

All subjects in the study must refrain from taking prohibited concomitant medications as outlined in Section [9.7.1](#).

Details of all prior medications (taken within 30 days of screening) and all current concomitant medication use (including herbal supplements), including all medications administered for the treatment of AEs, will be recorded in the source documentation /CRFs.

Subjects whose illness is being treated with C1-INH, tranexamic acid, or lanadelumab prophylaxis regimens are allowed to continue on their regimen; however, the Investigator is encouraged to assess response to BCX7353 therapy and reduce and/or discontinue prophylactic C1-INH, tranexamic acid, or lanadelumab use over time if clinically warranted.

Steady state levels of BCX7353 are reached with daily dosing between 6 and 12 days. Therefore, the following strategies are recommended for subjects who are beginning BCX7353 in place of another method of prophylaxis:

Table 2. Recommended Strategies for Switching to BCX7353 Prophylaxis from Another Therapy

Current Prophylactic Therapy	Timing of BCX7353 Initiation
Androgens (eg, danazol)	Discontinue androgens. Day 1 of BCX7353 dosing may occur a minimum of 28 days after the last dose of androgens. Androgens may be discontinued or tapered in accordance with the usual practice of the Investigator; however, last dose must occur a minimum of 28 days prior to BCX7353 initiation.
Tranexamic acid	Discontinue tranexamic acid dosing 14 days after first dose of BCX7353.
C1-INH (eg, Cinryze, Haegarda)	Discontinue existing C1-INH dosing schedule 14 days after first dose of BCX7353.
Lanadelumab-flyo	Day 1 of BCX7353 dosing to occur on same day as lanadelumab injection. No further dosing of lanadelumab is required after initiating BCX7353.

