## **6.4. Data Presentation Conventions**

Continuous variables (eg, age) are summarized using descriptive statistics (the number of subjects with available data, the mean, standard deviation (SD), median and minimum and maximum). Categorical variables (eg, race) are summarized using counts and percentages. Percentages are calculated using the total subjects per treatment group.

The following conventions are applied to all data presentations and summaries.

- For continuous variables, all mean and median values are formatted to 1 more decimal place than the measured value. SD values are formatted to 2 more decimal places than the measured value. Minimum and maximum values are presented with the same number of decimal places as the measured value.
- For categorical variables, the number and percentage of responses are presented in the form XX (XX.X%) where the percentage is in the parentheses.

- Date variables are formatted as DDMMYYYY for presentation. Time is formatted in military time as HH:MM for presentation.
- Wherever possible, data will be decimal aligned.

The table of contents as part of this SAP along with the table and listing shells provided in separate documents provide the expected layout and titles of the tables, listings and figures. Any changes to format, layout, titles, numbering, or any other minor deviation will not necessitate a revision to the SAP, nor will they be considered as deviations from planned analyses. Only true differences in the analysis methods or data handling will necessitate such documentation. The appropriate listings supporting the tables will be included and are not necessarily specified in the individual sections throughout the document.

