### **6.7.5. Subjects Entering the Study on Prophylactic HAE Medications**

Any subject who took Berinert, Ruconest, Haegarda, or Cinryze (all C1-inhibitors or C1-esterase inhibitors [C1-INH]) on Study Day 1 with regular frequency of administration (eg, once weekly, twice weekly, etc.) or tranexamic acid taken daily and *not* flagged on the concomitant medications eCRF as ‘PRN’ are considered to be on current prophylactic medication.

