#### **9.3.5. Summaries of Adverse Incidence Rates per 100 Person-Years of Exposure to Study Treatment**

For this study, the duration of exposure to study treatment may vary due to differential follow-up. Because of this, certain AE tables will be repeated using the number of AEs per 100 person-years of exposure instead of as a count, where 1 year = 365.25 days.

To determine 100 person-years of exposure, the duration of treatment exposure will be computed for each subject and then summed across subjects to obtain the 100 person-years exposure per treatment group. The table will then display the rate per 100 person-years of exposure (count of AEs reported/total exposure for the treatment group in 100 person-years) values for each treatment group and for each AE.

The following summary tables of rate of TEAEs per 100 person-years of exposure will be provided by treatment group (by SOC and PT):

- Summary of TEAE rate per 100 person-years of exposure
- Summary of drug-related, TEAE rate per 100 person-years exposure
- Summary of TESAEs

A listing of 100 person-years of exposure to study treatment will be provided.

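### The one TEAE table on BCX7353 with background prophylaxis (SAP Table 14.3.1.48) counts events only during overlap but has no overlap-time denominator, so its percentages tend to fall as overlap shortens

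*SAP*

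**What the plan says.** **The table.** SAP 9.3.1 states: "A single presentation of the summary of TEAEs for subjects entering on prophylactic medications will be presented". It then restricts the events: "For this presentation, only TEAEs occurring while the subject was simultaneously taking BCX7353 and prophylactic medication will be summarized". The display list in SAP 13.1 has one matching table, 14.3.1.48, and a listing, 16.2.7.11. The TEAE summaries of SAP 9.3.1 are introduced so: "The following summary tables (number and percentage of subjects) of TEAEs (by SOC and PT) will be provided by treatment group". Event counts are added to every TEAE table except the overall summary. By contrast, SAP 9.3 runs the general TEAE window from first dose to 30 days after treatment ends.

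**Denominators.** The general convention in SAP 6.4 reads: "Percentages are calculated using the total subjects per treatment group". Nothing specific is stated for Table 14.3.1.48. SAP 9.3.5 gives the reason for person-year rates, namely that "the duration of exposure to study treatment may vary due to differential follow-up". The display list applies them to the AE tables 14.3.1.45 to 14.3.1.47 (overall and by androgen subgroup) and to liver-test elevations (14.3.5.25.1 to 14.3.5.25.3). No person-year version of 14.3.1.48 is listed.

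**Length of overlap.** Protocol Table 2, a set of recommendations for subjects replacing another prophylaxis, says for C1-INH: "Discontinue existing C1-INH dosing schedule 14 days after first dose of BCX7353". It gives the same interval for tranexamic acid. Protocol 9.7 also lets subjects stay on their regimen, with reduction over time at the investigator's judgement. SAP 7.7 plans a Kaplan-Meier estimate of time to stopping prophylaxis and censors subjects who never stop.

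**Who is counted.** SAP 6.7.5 defines the group by a named C1-INH product taken "on Study Day 1 with regular frequency of administration (eg, once weekly, twice weekly, etc".), or by daily tranexamic acid not flagged as taken as needed.

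**The concern.** The share of subjects with at least one event grows with time at risk. Table 14.3.1.48 cuts the time at risk to the overlap, and then reports a share of subjects without saying how long the overlap was. A reader will naturally set it beside the all-subjects TEAE table, where time at risk is the whole of treatment. A lower percentage could then reflect a shorter window and nothing else, and a real excess during overlap could be hidden by the same mechanism.

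This matters because Protocol 5.4.3 says that the current version is meant to supply data for guidance on switching from other prophylaxis. This is the only TEAE table planned on the overlap. SAP 9.3.5 already recognises that exposure varies, but its remedy is not applied to the table whose window is deliberately cut.

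**Working it through.** The documents give no expected incidence during co-use and no sample size calculation, so there is no planned figure to reproduce. The check asks how far the window alone can move the percentage.

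**Inputs (Protocol 5.2.2, interim data)**
- Any TEAE: 91.0% of 100 subjects (110 mg) and 90.6% of 127 (150 mg). That is 91 + 115 = 206 of 227 = 90.7%.
- Drug-related TEAE 49.8%; Grade 3 or 4 TEAE 15.0%; treatment-emergent SAE 13.2%.
- Mean exposure T = 282.7 days (range 11 to 540).
- Overlap of 14 days from Protocol Table 2; longer overlaps are tried because Protocol 9.7 allows them.

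**Model.** P(t) = 1 − exp(−H × (t/T)^k), with H = −ln(1 − p) and p the interim incidence. Assumptions: everyone has the mean exposure, and the hazard is the same with and without co-use. k = 1 is a constant hazard; k = 0.5 and k = 0.3 are early-loaded alternatives.

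**Any TEAE at 14 days**
- H = −ln(1 − 206/227) = 2.380; at k = 1 this is 2.380/282.7 = 0.00842 per day.
- k = 1: 1 − exp(−14 × 0.00842) = 11.1%.
- k = 0.5: 41.1%. k = 0.3: 61.9%.

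**The same step for the other outcomes at 14 days**

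| Outcome | Interim | k = 1 | k = 0.5 | k = 0.3 |
|---|---|---|---|---|
| Any TEAE | 90.7% | 11.1% | 41.1% | 61.9% |
| Drug-related | 49.8% | 3.4% | 14.2% | 24.4% |
| Grade 3 or 4 | 15.0% | 0.8% | 3.6% | 6.4% |
| SAE | 13.2% | 0.7% | 3.1% | 5.6% |

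**Hazard ratio needed for the 14-day percentage to equal the full-exposure one.** (282.7/14)^k = 20.2 (k = 1), 4.5 (k = 0.5), 2.5 (k = 0.3).

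**Dependence on the length of overlap (any TEAE, k = 1).** 28 days 21.0%; 84 days 50.7%; 168 days 75.7%; 282.7 days 90.7%.

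**Mixed pattern.** If a share f stops at 14 days and the rest continue to 282.7 days, the percentage is f × 11.1 + (1 − f) × 90.7. It is 70.8% for f = 25%, 50.9% for 50% and 31.0% for 75%. For f = 0 it is 90.7%, so there is no distortion.

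**Effect of a time denominator.** At constant hazard the first-TEAE rate is 0.00842 × 365.25 × 100, about 308 per 100 person-years, for a 14-day or a 282.7-day window alike. If events are early-loaded, the rate in a short early window is higher than the full-exposure rate, so person-years alone do not make the two comparable. The matching comparison is the same early study days in subjects without prophylaxis.

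**Day 1 wording.** Read literally, and if infusion days are independent of Study Day 1, the rule captures 1/7 = 14% of once-weekly and 2/7 = 29% of twice-weekly C1-INH users.

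**The case against.** **Fourteen days is not established as the usual overlap.** A reader might infer from Protocol Table 2 that typical co-exposure is about two weeks. The documents do not support that. The table is a recommendation for switchers, continuation is allowed, and SAP 7.7 provides for subjects who never stop. The revision history in SAP Table 2 also ends at Protocol Version 5.0, whereas the 14-day advice is read here from the later, 150 mg-only protocol. The interim exposure comes from 22 countries, and Protocol 5.4.3 describes the study to that point as conducted mainly outside the US, in many areas where long-term prophylaxis is uncommon. This objection stands, and it is why the size is given as a range.

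**There is no comparison with BCX7353 alone.** A reader might infer that co-use will look safer than BCX7353 alone. The SAP plans no such table. The nearest comparator is the all-subjects table, which includes the co-users. With long co-use, or a higher hazard during it, the gap shrinks or disappears. This stands too.

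**Other displays help.** The Kaplan-Meier estimate of time to stopping prophylaxis, the listing of AEs in these subjects and the planned event counts let a careful reader see that exposure was short. This stands in part: none of them puts person-time beside the events.

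**The denominator may be obvious.** The title of Table 14.3.1.48 suggests that only subjects entering on prophylaxis are counted, and the table shells are separate documents. That is plausible, so dilution by the whole dose group is a risk of the SAP 6.4 default and not a certainty.

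**The Day 1 rule has a benign reading**, namely a regular regimen current on Study Day 1. A reader might infer that the table will cover only a minority of co-users. That needs the literal reading plus independence of infusion days, and it leaves out daily tranexamic acid users. It also concerns who is counted, not how long they are exposed.

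**Conclusion.** The concern holds as a reporting defect in one descriptive safety table: its event window is cut to simultaneous use and its percentage has no matching time denominator. To the extent that co-use is short, the figure is likely to be lower than in the all-subjects table at the same underlying risk.

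The size runs from no distortion, if co-use lasts as long as treatment, to a fall from 90.7% to between about 11% and 62% if everyone stops at 14 days. These figures rest on equal hazards, a single mean exposure for all subjects and the assumed hazard shapes. Exposure actually ranged from 11 to 540 days, so they show scale and are not predictions. The direction is the same under every shape tried.

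The Day 1 wording in SAP 6.7.5 is a separate and smaller selection ambiguity. How long the overlap should last is a clinical matter and is not judged here.

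**What to change.** 1. In SAP 9.3.1, state that the denominator of Table 14.3.1.48 is the number of subjects entering on prophylaxis in each dose group.
2. In SAP 9.3.1 and 9.3.5, add to that table the total days of concurrent exposure and events per 100 person-years of concurrent exposure.
3. Beside it, show descriptively the rate over the same early study days (for example Days 1 to 14) in subjects without prophylaxis, because person-years alone do not remove early loading.
4. In SAP 6.7.5, define the group by a regular-frequency prophylaxis record that started on or before Study Day 1 and had not stopped before it.

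The cost is SAP wording and one extended descriptive table. Medication start and stop dates are already collected on the eCRF, and the person-year method is already in the SAP. Nothing changes in treatment or data collection. If few subjects co-use, the rates will be imprecise; the stated person-time will make that visible.
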